### **Reporting to UCSF Committee on Human Research (Institutional Review Board)**

The Principal Investigator must report events meeting the UCSF CHR definition of “Unanticipated Problem” (UP) within 5 business days of his/her awareness of the event.

### **Expedited Reporting to the Food and Drug Administration**

If the study is being conducted under an IND, the Sponsor-Investigator is responsible for determining whether or not the suspected adverse reaction meets the criteria for expedited reporting in accordance with Federal Regulations (21 CFR §312.32).

The Investigator must report in an IND safety report any suspected adverse reaction that is both serious and unexpected. The Sponsor-Investigator needs to ensure that the event meets all three definitions:

- Suspected adverse reaction
- Unexpected
- Serious

If the adverse event does not meet all three of the definitions, it should not be submitted as an expedited IND safety report.

The timeline for submitting an IND safety report to FDA is no later than **15 calendar days** after the Investigator determines that the suspected adverse reaction qualifies for reporting (21 CFR 312.32(c)(1)).

Any unexpected fatal or life-threatening suspected adverse reaction will be reported to FDA no later than **7 calendar days** after the Investigator's initial receipt of the information (21 CFR 312.32(c)(2)).

Any relevant additional information that pertains to a previously submitted IND safety report will be submitted to FDA as a Follow-up IND Safety Report without delay, as soon as the information is available (21 CFR 312.32(d)(2)).

### **Reporting SAEs to Pharmaceutical Companies providing Study Drug**

All expedited SAEs (serious, unexpected and related to study drugs) must be reported to Bavarian Nordic within 24 hours by fax or email to:

Bavarian Nordic

[REDACTED]

Specify: protocol #, subject #, PI name/site#, SAE/onset dates

In addition, all SAEs – serious, unexpected, and related to ipilimumab – must be reported to Bristol-Myers Squibb, Inc. within 24 hours by fax or email to:

Bristol-Myers Squibb Company Global Pharmacovigilance & Epidemiology Department

[REDACTED]

## Reporting Non-Serious AEs to Pharmaceutical Companies providing Study Drug

All non-serious AEs should be transferred to Bavarian Nordic and Bristol-Myers Squibb, Inc. (related to ipilimumab), every six months once the case is closed in the UCSF safety database.

## 8 Statistical Considerations and Evaluation of Results

### 8.1 Study Endpoints

See section 2.4 for endpoints.

### 8.2 Sample size and power estimate

The primary endpoint is the proportion of patients who demonstrate a positive response to neoadjuvant therapy for each arm of the study. A positive response is defined as a  $\geq 2$ -fold increase in the number of infiltrating CD3+ T cell between the pretreatment biopsy and the post-treatment RP specimen. A negative response is defined as a  $< 2$ -fold increase. We expect treated patients have more positive responders than the reference cohort with no neoadjuvant treatment (see section 8.6); thus we consider the lower threshold for the probability of positive responders to be 5%. If the true proportion of positive responders is 25%, with 13 patients in each treatment arm, we will have 90% confidence interval of (6.6%, 49.5%). Considering a dropout rate of 7%, a total of 42 patients will be accrued to the study. Additionally, with 13 evaluable patients in each arm, we have 80% power to detect a significantly different response rate between the PROSTVAC and ipilimumab combination arm versus the two monotherapy arms, at a significance level of 0.1, if the monotherapy arms have an average response rate of 20% and the combination arm has a response rate of 66%.

Patients who complete screening but withdraw prior to receiving treatment will be replaced. There are no stratification factors in this analysis.

### 8.3 Accrual

It is anticipated that 4 subjects will be enrolled on study each month, with accrual to the study completed in approximately 18 months. With 12 months of planned follow-up after RP, the study is expected to be completed in 30 months.

## 8.4 Interim Analyses and Stopping Rules

There will be no formal interim analysis for efficacy performed in this study. Please refer to section 5.1.1 regarding criteria for stopping treatment for lack of safety.

## 8.5 Analyses Plans

Safety analyses will be performed on safety-evaluable patients, defined as enrolled patients who received any amount of the study treatment. Efficacy analyses will be performed on efficacy-evaluable patients, defined as safety evaluable patients with measurable disease at baseline.

Demographic and baseline characteristics will be summarized by arm and overall. In general, frequency distribution and percentage will be used to summarize categorical measurements, while mean (with standard deviation) and median (with range) will be used to describe symmetric and skewed continuous measurements, respectively. Univariate analysis among variables will be assessed using the two-sample t-test, Wilcoxon-rank-sum test, Chi-square test, as appropriate.

### 8.5.1 Primary Analysis (or Analysis of Primary Endpoint)

The primary analysis for immune response within the prostate will include all enrolled subjects who receive at least 1 dose of PROSTVAC or ipilimumab in any of the treatment arms, and undergo RP. Analysis will be done for each arm separately as well as aggregate for all treatment arms.

CD3+ T cell infiltration will be assessed by IHC staining, and quantitated by the number of CD3+ T cells/ $\mu\text{m}^2$ . Therefore, the number of T cells will be normalized per unit area. For the analysis of the primary endpoint, T cells will be enumerated from tumor/benign tissue interface (from here on referred to as the “tumor interface”). Subjects will be considered to have a “positive” response if they exhibit a  $\geq 2$ -fold increase in CD3+ T cell infiltration, and a “negative” response if they exhibit a  $< 2$ -fold increase. The proportion of patients who have “positive” responses will be reported, with 95% confidence intervals. Furthermore, the positive response rate will be compared between the combination arm vs. the monotherapy arms (pooling the two monotherapy arms together) via two-sample proportion test. Pairwise comparisons among the three arms will also be performed by two-sample proportion test. No multiple testing adjustments will be performed. Additional analyses will be performed for assessment of response at the tumor center and benign glands and will be reported similarly to the primary endpoint.

### 8.5.2 Secondary Analyses (or Analyses of Secondary Endpoints)

- T cell tumor infiltration (of selected T cell subsets) will be scored by IHC assessment, and scored by the number of T cells/ $\mu\text{m}^2$ . Therefore, the number of T cells will be normalized per unit area. The change in T cell infiltration following neoadjuvant therapy will be determined as described above for the primary endpoint. Similar analyses may be performed for other immune cells, such as CD4+, CD8+, CD56+, FOXP3, etc. Results will be reported as described for the primary endpoint, and T cell infiltration will be reported separately for areas of tumor interface, tumor center and benign tissue.
- Flow cytometry will be performed in both pre- and post-treatment peripheral blood mononuclear cells (PBMC) to determine the change in T cell activation (both  $\text{T}^{\text{reg}}$  and  $\text{T}^{\text{effector}}$  cells) after neoadjuvant therapy. Descriptive statistics for continuous measurements will be used to summarize the changes.
- Treatment-related toxicities will be assessed according to NCI CTCAE v4.03, for all patients who receive at least a single dose of investigational therapy. The distribution for the

maximum observed grade for each adverse event will be tabulated and reported with 95% confidence interval.

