### 1.3 Ipilimumab

Inhibition of immune checkpoints represents another important major strategy in prostate cancer immunotherapy (Figure 2). Cytotoxic T lymphocyte-associated antigen 4 (CTLA-4) is a molecular “brake” on the immune system. The cell-surface molecule is found on activated T cells and interfaces with the B7 ligands, CD80 and CD86, on antigen presenting cells (APCs). CTLA-4

binds more avidly to the B7 ligands than CD28 receptors, which are responsible for costimulatory signaling, and leads to negative regulation of T-cell activation and proliferation. CTLA-4 also is expressed constitutively on T-reg cells, which contribute to the induction of peripheral self-tolerance.

Ipilimumab is a human immunoglobulin G (IgG1)κ anti-CTLA-4 monoclonal antibody (mAb). *In vitro* studies were performed with ipilimumab to demonstrate that it is specific for CTLA-4, actively inhibits CTLA-4 interactions with B7.1 and B7.2, does not show any cross-reactivity with human B7.1, B7.2 negative cell lines, and stains the appropriate cells without non-specific cross-reactivity in normal human tissues, as demonstrated by immunohistochemistry.

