#### 2.4.2 Secondary Endpoints

[figure not shown]
- The change in immunologic infiltration in tumor tissue quantitated by IHC assessment (e.g. CD4+, CD8+, CD56+, FOXP3, etc.) following neoadjuvant PROSTVAC or ipilimumab or the combination
- Change in circulating effector and regulatory T cells following neoadjuvant PROSTVAC or ipilimumab or the combination by flow cytometry assessment of peripheral blood mononuclear cells
- Treatment related toxicities according to NCI CTCAE v.4.03

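### Section 8.5.2 carries the primary endpoint's increase-only responder rule over to tissue FOXP3, so a fall in regulatory T cells scores the same as no change

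*Combined protocol and SAP*

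**What the plan says.** Section 2.4.2 defines the tissue secondary endpoint as "The change in immunologic infiltration in tumor tissue quantitated by IHC assessment (e.g. CD4+, CD8+, CD56+, FOXP3, etc". It is a change, and no direction is given for any marker.

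Section 8.5.2 supplies the method by cross-reference. For T cell subsets, "The change in T cell infiltration following neoadjuvant therapy will be determined as described above for the primary endpoint". It then adds: "Similar analyses may be performed for other immune cells, such as CD4+, CD8+, CD56+, FOXP3, etc. Results will be reported as described". The reference is again to the primary method, with results given separately for tumor interface, tumor center and benign tissue.

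The method referred to is in Sections 8.2 and 8.5.1. A response is positive if there is at least a 2-"fold increase in the number of infiltrating CD3+ T cell between the pretreatment biopsy and the post-treatment RP specimen"; anything less is negative. Then: "The proportion of patients who have “positive” responses will be reported, with 95% confidence intervals". Arms are compared as combination against monotherapy ("pooling the two monotherapy arms together) via two-sample proportion test") and pairwise.

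Nowhere do the documents give tissue FOXP3 its own direction, a category for decreases or a dedicated continuous summary. On the biology, Section 1.3 says: "CTLA-4 also is expressed constitutively on T-reg cells, which contribute to the induction of peripheral self-tolerance".

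**The concern.** The cut-off was written for CD3+ infiltration, where the study hypothesis (Section 1.4) is recruitment, so looking only for a rise makes sense. FOXP3 marks a regulatory population, and its endpoint is a change in either direction. An increase-only cut-off records one half of that endpoint and merges the other half with no change. It also attaches the words *positive response* to a rise in regulatory cells, which invites a reading that the plan does not intend or explain.

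Two of the three arms (B and C) receive an antibody against CTLA-4, which the protocol says regulatory T cells express constitutively. A fall in tissue FOXP3 is therefore a result that the trial should be able to display. If the direction of interest is settled only after the data are seen, the FOXP3 result becomes post hoc.

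**Working it through.** **1. The rule applied to single patients.** Let R be the post/pre density ratio (Section 7.1.1 defines it for CD3+). Positive means R ≥ 2; negative means R < 2.

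| FOXP3 pre → post (illustrative) | R | Score |
|---|---|---|
| 50 → 200 | 4.0 | positive |
| 100 → 100 | 1.0 | negative |
| 200 → 100 | 0.5 | negative |
| 200 → 50 (75% fall) | 0.25 | negative |

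The last three rows cannot be told apart. This follows from the rule alone and needs no model.

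**2. The plan's own figures.** Section 8.2 states 80% power with 13 per arm, 20% v 66%, significance level 0.1. The normal-approximation two-proportion test, 13 v 13 and two-sided, gives 79.3%, so these settings match the plan and are used below (the plan does not state sidedness). The exact 90% interval for 3/13 is 6.6% to 49.5%, as stated. For accrual, 13/0.93 = 13.98, rounded up to 14 per arm, or 42 in total. None of these figures is in dispute, and none concerns FOXP3.

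**3. What the rule does at arm level.** The documents give no FOXP3 variability. Assume log2 R is normal with mean m and SD s. No change is m = 0; a median halving is m = −1.

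- Share positive under no change: P(Z ≥ 1/s)
- Share positive under halving: P(Z ≥ 2/s)
- Share with a fall of at least 2-fold: P(Z ≤ −1/s) = P(Z ≥ 1/s) under no change, and P(Z ≤ 0) = 50% under halving

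Power is an exact binomial enumeration of the pooled two-sample proportion z-test, 13 v 13, two-sided alpha 0.1, for an arm with halved FOXP3 against an arm with no change.

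| s | Positive, no change | Positive, halving | Power, increase rule | Power, decrease category |
|---|---|---|---|---|
| 0.6 | 4.8% | <0.1% | 2% | 90% |
| 1.0 | 15.9% | 2.3% | 26% | 61% |
| 1.5 | 25.2% | 9.1% | 30% | 36% |

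At s = 0.6 the increase rule's power (2.2%) is no higher than its rejection rate when both arms are unchanged (2.3%).

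**4. A second calibration.** Set s so that no change gives 5% positives (s = 1/1.645 = 0.608) or 20% (s = 1/0.842 = 1.188). Power is then 2.4% v 89.7% and 30.7% v 49.5%, increase rule against decrease category. At the 5% base, 0 of 13 positives has probability 0.95^13 = 51% under no change and 99% under a median halving, so seeing 0/13 hardly separates the two.

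**5. The mirror image.** The model is symmetric. If treatment doubles FOXP3, a decrease-only test has 2%, 26% and 30% power at s = 0.6, 1.0 and 1.5, and the existing rule has 90%, 61% and 36%. Replacing one direction by the other only moves the blind spot.

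**The case against.** Several points on the other side are sound.

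- **The wording is permissive.** Section 8.5.2 says FOXP3 analyses *may* be done and calls them *similar*; no FOXP3 threshold is written. This is a gap left by a cross-reference more than a deliberate scoring choice. Even so, if FOXP3 is analysed, no other tissue method is specified.
- **A reader might infer that the rule is backwards for FOXP3.** The documents do not support that. They never call a FOXP3 positive favourable, Section 2.2 sets out only to characterize tissue subsets, and a 2-fold rise correctly records recruitment. The supportable criticism is that the rule sees one direction only.
- **A reader might infer that a named regulatory T cell objective goes unserved.** It does not. The objective in Section 2.2 that names regulatory T cells concerns circulating cells, and Section 8.5.2 summarises those with continuous descriptive statistics, which show both directions.
- **Depletion is not the protocol's hypothesis.** Section 1.4 speaks of recruitment, and Section 1.3.1 reports no depletion of T cell subsets in monkeys. The halving is an assumption made to test the rule, not a prediction.
- **The raw data would show a fall.** Section 7.1.2.1 says subset change will be assessed, and Section 8.5 describes means and medians for continuous measurements in general. Nothing forbids reporting the FOXP3 ratio; Section 8.5.2 simply does not call for it.

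These points limit the weight of the finding. They do not alter the scoring in step 1.

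**Conclusion.** The point holds in a limited form. If tissue FOXP3 is analysed as Section 8.5.2 describes, the reported proportion captures rises of at least 2-fold and gives every fall the same score as no change. That misses part of an endpoint defined as change.

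For each patient this is exact. At arm level its size depends on an unknown SD: about 2% to 30% power to detect a median halving, against 90% to 36% with a decrease category, for s from 0.6 to 1.5. Those figures rest on a normal log2 ratio, 13 v 13 patients and two-sided alpha 0.1. It would be too strong to say that a fall is always invisible: that is nearly so at s = 0.6, but at s = 1.5 the two rules differ only modestly. The SD near 0.6 is tied to the 5% in Section 8.2, which is a lower threshold for CD3+ responders and not an observed FOXP3 rate.

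One optional marker within a secondary endpoint is affected, and no decision rule depends on it. The primary analysis, sample size and power stand.

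**What to change.** In Section 8.5.2, exempt FOXP3 from the positive/negative response label and state that, for each tissue location:

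- the post/pre density ratio is reported by arm as median and range;
- patients are tabulated in three categories: fall of at least 2-fold, within 2-fold, rise of at least 2-fold;
- arms are compared on the ratio by a method that responds to either direction, such as the Wilcoxon rank-sum test already named in Section 8.5, and not on the rise or the fall alone.

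A CD8:FOXP3 density ratio is an optional addition. The cost is one sentence and one table, with no new data wherever FOXP3 is counted.

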### 8.5.3 Exploratory Analyses (or Analyses of Exploratory Endpoints)

- To characterize antibody responses to a broad panel of antigens, sera will be collected at baseline, prior to RP, and 9 weeks following RP, and profiled using spotted antigen array (50). After standard preprocess of the protein array data, Cluster and Tree view software will be used for unsupervised clustering of the data with Pearson correlation and complete linkage. For each array, an antigen is identified as being detected if its value is above the median. To determine the number of up- and down-modulated antibodies, the difference in log2 intensity values of pretreatment and post-treatment samples will be taken for each patient to identify antigens that are detected differentially due to treatment.
- Assessment of change from baseline in antigen-specific T-cell immunity in the blood will be performed using repeated measure analysis of variance (ANOVA) methods with a mixed model approach to allow for a varying number of follow-up measurements. To study the change from baseline (screening visit) to post-baseline visits (up to 9 weeks post-RP), the mixed model will include four visits (up to 9 weeks post-RP) and subject as a random effect. Using polynomial contrast statements, the overall pattern T-cell immunity in the blood (e.g. linear) will be investigated. The specific comparison of change in immunity between baseline and any specific post-baseline time point will be tested also using linear contrast statements. The above analysis will be done for each arm separately as well as aggregate.
- Development of and changes in humoral immune responses in the periphery following treatment. This will be evaluated by testing serum with methods such as:
  - Measurement of antibodies to PSA, TAA and the viral vector may be performed using peptide/protein arrays, standard ELISA assays or flow cytometry to determine neutralizing antibody titers. After standard pre-process of the protein array data, Cluster and Tree view software will be used for unsupervised clustering of the data with Pearson correlation and complete linkage. For each array, an antigen is identified as being detected if its value is above the median. To determine the number of up- and down-modulated antibodies, the difference in log2 intensity values of pre-treatment and post-treatment samples will be taken for each patient to identify antigens that are detected differentially due to treatment.
  - Measurement of cytokines, chemokines or cancer biomarkers by Luminex multiplex analysis will be summarized by descriptive statistics for continuous variables at each timepoint for each arm. Furthermore, repeated measure ANOVA methods with a mixed model approach to allow for a varying number of follow-up measurements will be applied. The specific comparison of change between baseline and any specific post-baseline time point will be tested also using linear contrast statements.
  - PD-L1 expression, by IHC assessment, will be scored on a 0-3 scale (0=0-5% staining, 1=6-33% staining, 2=34-66% staining, 3=67-100% staining). For each subject, the change in PD-L1 expression score following neoadjuvant therapy will be calculated for exploratory characterization of the impact on PD-L1 in localized prostate cancer. Descriptive statistics for categorical measurements will be used to summary the PD-L1 expression change for each location. Furthermore, univariate analysis (proportion test) will be applied to explore the PD-L1 expression score change between locations.
- In order to assess the clinical impact of neoadjuvant treatment with PROSTVAC, ipilimumab, or the combination or PROSTVAC and ipilimumab:

- The proportion of patients who achieve a  $\geq 30\%$  decline in PSA at the time of RP will be reported with 95% confidence intervals.
- The proportion of patients with pathologic complete response (pT0) at the time of RP will be reported with 95% confidence intervals.
- T-cell receptor (TCR) repertoire sequencing following re-stimulation on T cells in vitro with prostate specific, tumor associated antigens and vector specific antigens to evaluate clonality of T-cell responses in the periphery. The responses in the tumor may also be evaluated in prostate biopsy samples to allow correlation with responses in the periphery. For each individual treatment, the change in tumor-infiltrating TCR between pre-treatment and post-prostatectomy after treatment will be assessed by calculating the number of unique clonotypes comprising the top 25th percentile of cumulative reads after sorting by clone abundance. Repertoire change between sequencing experiments will be measured using Morisita's distance.

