### 2.4.3 Exploratory Endpoints

- Change in antigen-specific T cell responses in peripheral blood from baseline (screening visit) to post-RP (9 weeks post-RP visit) assessed by using a T cell proliferation assay, and interferon gamma (IFN- $\gamma$ ) immunospot (ELISPOT) assays. In a limited number of patients we will also assess for antigen-specific T cells in tumor infiltrating lymphocytes isolated from the RP as fresh tissue is available.
- Development of and changes in humoral immune responses in the periphery following treatment. This will be evaluated by testing serum with methods such as:
  - Measurement of antibodies to PSA,TAA and the viral vector using peptide/protein arrays or standard ELISA assays.
- To characterize the frequency of circulating B and T cells induced by neoadjuvant PROSTVAC or ipilimumab or the combination in patients with localized prostate cancer by flow cytometry. In a limited number of patients we will also assess for antigen-specific T cells in tumor infiltrating lymphocytes isolated from the RP as fresh tissue is available.
- T-cell receptor (TCR) repertoire sequencing following restimulation with prostate specific tumor-associated antigens and viral vector specific antigens to evaluate clonality of T-cell responses in the periphery. TCR repertoire in the tumor may also be evaluated in prostate biopsy samples to allow correlation with responses in the periphery.
- Change in PD-L1 expression by IHC assessment following neoadjuvant PROSTVAC or ipilimumab or the combination
- The clinical benefit of neoadjuvant PROSTVAC or ipilimumab or the combination as measured by:
  - Proportion of patients with a PSA response ( $\geq 30\%$  PSA decline) at the time of RP.
  - Proportion of patients with pathologic complete response (pT0) or near complete response at the time of RP.

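### The per-array median rule calls about half of all antigens detected on every array, so the detection call cannot show presence, development or breadth of an antibody response

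*Combined protocol and SAP*

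**What the plan says.** Section 2.4.3 lists as an exploratory endpoint: "Development of and changes in humoral immune responses in the periphery following treatment". Section 8.5.3 gives the array analysis in two places, once for a broad antigen panel and once for antibodies to PSA, tumour-associated antigens and the viral vector. The first opens: "To characterize antibody responses to a broad panel of antigens, sera will be collected at baseline, prior to RP, and 9 weeks following RP".

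Both places use the same steps:

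- **Preprocessing and clustering.** "After standard preprocess of the protein array data, Cluster and Tree view software will be used for unsupervised clustering" (first paragraph; the second is nearly identical). What standard preprocessing includes is not stated.
- **Detection.** "For each array, an antigen is identified as being detected if its value is above the median". No negative-control, background or pooled-baseline reference is named.
- **Change with treatment.** "To determine the number of up- and down-modulated antibodies, the difference in log2 intensity values of pretreatment and post-treatment samples will be taken". This is done within each man, and the stated purpose is "to identify antigens that are detected differentially due to treatment". No log2 cut-off is given, and the text does not say how this step uses the detection call.

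For the second group of antibodies other assays are allowed: "Measurement of antibodies to PSA, TAA and the viral vector may be performed using peptide/protein arrays, standard ELISA assays or flow cytometry".

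**The concern.** A detection rule should separate signal from background. A cut-off at each array's own median only ranks antigens within that array. It labels about half the panel detected even on an array that holds nothing but noise, and the number detected cannot rise after treatment.

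The endpoint covers the development of humoral responses, which means antigens going from undetected to detected, and the stated aim is a broad panel. The median call is the only criterion in the array text for whether an antibody is present. If it is used for presence, for new responses or for breadth, the answer is fixed in advance. If differential detection is read as a change in this call, real gains also produce false losses among antigens whose antibodies did not change.

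**Working it through.** **Inputs from the plan.** The detection rule, the log2 difference and the three serum times come from section 8.5.3; the exploratory status comes from section 2.4.3. The plan gives no panel size, preprocessing method, log2 cut-off, power or expected result for this analysis, so there is no figure to reproduce.

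**Step 1: the count is fixed.** Among m untied values, the number above their own median is floor(m/2), whatever the values are.
- m = 1,000 gives 500, or 50.0%.
- m = 101 gives 50, or 50/101 = 49.5%.

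**Step 2: gains equal losses.** Detected after = detected before + gained − lost. Both counts are floor(m/2), so gained = lost on every pair of arrays. Steps 1 and 2 need no distributional assumption.

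**Step 3: false losses (illustration).** Assume 1,000 antigens, normal log2 intensities in SD units and pre/post correlation r = 0.95.
- With no effect, the share changing status is arccos(r)/π = arccos(0.95)/π = 10.1%, that is 5.1% gained and 5.1% lost. At r = 0.90 the share changing is 14%, and at r = 0.80 it is 20%.
- Raise 200 antigens by 1 SD. The post-treatment median c solves 0.8·[1 − Φ(c)] + 0.2·[1 − Φ(c − 1)] = 0.5, so c = 0.184. For an unchanged antigen, P(before > 0 and after < 0.184) = 9.5%. That is 0.095 × 800 = 76 antigens scored as lost, against 0.0505 × 800 = 40 from noise alone.
- Raise 600 antigens: c = 0.608, and 23% of the 400 unchanged antigens are scored as lost.
- In each case 500 antigens are detected. With a cut-off held at the pre-treatment median, the expected counts are 800 × 0.5 + 200 × 0.841 = 568, 400 × 0.5 + 600 × 0.841 = 705, and 841 if all rise. Losses among unchanged antigens stay at 5.1%.

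**Step 4: does the log2 difference still work?** This is a simulation under further assumptions: 1,000 antigens, between-antigen SD 1.5 and technical SD 0.3 (log2 units), a fraction f raised by 2 log2 units, 200 repeats. A change is counted at an assumed cut-off of 1 log2 unit. Entries are percentages of the panel.

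| f | Detected after, own median | Gained / lost | Up / down on log2, not centred | Up / down on log2, median-centred | Detected after, fixed cut-off, not centred |
|---|---|---|---|---|---|
| 0% | 50.0 | 4.4 / 4.4 | 0.9 / 0.9 | 0.9 / 0.9 | 50.0 |
| 10% | 50.0 | 6.3 / 6.3 | 10.8 / 0.9 | 10.1 / 2.1 | 54.1 |
| 30% | 50.0 | 10.2 / 10.2 | 30.4 / 0.7 | 25.6 / 10.3 | 62.2 |
| 50% | 50.0 | 12.2 / 12.2 | 50.2 / 0.5 | 24.9 / 25.1 | 70.3 |
| 80% | 50.0 | 8.2 / 8.2 | 79.6 / 0.2 | 5.1 / 18.8 | 82.4 |
| 100% | 50.0 | 4.5 / 4.5 | 99.1 / 0.0 | 1.0 / 1.0 | 90.5 |

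Without centring, the log2 difference tracks the response closely. With median-centring it still shows a response in a minority of antigens but fails once about half the panel rises. A cut-off fixed at the pre-treatment median is also defeated by median-centring: detection then returns to 50.0% at every f.

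**The case against.** A reader might infer that a broadened antibody response cannot be seen at all, or that the whole humoral result is uninformative. The documents do not support that. The sentence after the detection rule counts raised and lowered antibodies from within-patient log2 differences, which do not need the median call, and Step 4 shows that this measure can reveal a broad response. ELISA and flow cytometry are also permitted for PSA, tumour-associated and vector antibodies, and neither depends on an array median. This objection stands, and it limits the point to the detection call.

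The plan also never says that it will count detected antigens, compare the counts between visits or arms, or read them as breadth. The median call might be meant as an intensity filter, or some other median might be meant. That is fair: the harm depends on how the call is used. But the plan gives the call no other role, places it directly before a sentence about differential detection, and leaves the link between the two undefined. If another median is intended, the text must say which.

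The panel size, correlation and effect sizes above are assumptions. That is correct, but the constant half and the equality of gains and losses do not depend on them.

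The log2 difference is not a complete substitute for a detection rule. It measures change rather than presence, so an antigen moving within background can count as raised. If the unspecified preprocessing centres arrays on their median, a rise across about half the panel or more is lost there too.

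**Conclusion.** The point holds for the detection call. On the plain reading of the rule, about half the antigens are detected on every array and gains equal losses. The call therefore cannot inform on presence, development or breadth. This is arithmetic and assumes only that values are essentially untied. The size of the false-loss problem (9.5% against 5.1% of unchanged antigens when 200 of 1,000 rise by 1 SD at r = 0.95) is illustrative, and it matters only if differential detection uses the median call, which the text neither says nor excludes.

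The log2 analysis can still detect a response, subject to the unstated preprocessing and cut-off. The analysis is exploratory, with no error rate, power or decision attached. The correction is worth making because the rule appears twice, is wrong as a detection criterion, and costs little to replace.

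**What to change.** In both array paragraphs of section 8.5.3:

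1. Replace the array median with a cut-off that is the same before and after treatment, based on negative-control or background spots on the array. The documents do not say whether the array has them.
2. Where there are none, use a fixed cut-off per antigen from the pooled pre-treatment sera, and report it only as gain relative to baseline, not as presence at baseline. The limit is real. With mean + 3 SD of the same men's baseline values, the one-sided Chebyshev bound is 1/(1 + 3²) = 10%, so at most 4 of 42 men (42 × 0.10 = 4.2) could be above it at baseline for any antigen, however common the antibody.
3. Report the paired change in the number detected per man, by arm, alongside the log2 differences.
4. State the preprocessing, and do not median-centre arrays in a way that removes a broad rise. State the log2 cut-off, and say whether differential detection means a log2 change or a change in the detection call.

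The cost is SAP wording and re-coding one cut-off. No new samples or assays are needed, and the primary analysis and sample size do not change.
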